### **13.2 Patient Demographics and Other Baseline Characteristics**

The clinical and sociodemographic characteristics of the patients who are enrolled and treated on this study will be summarized by arm. Frequencies and percentages will be provided for categorical variables;

means and standard deviations or medians and interquartile ranges will be provided for continuous variables.

### **13.3 Treatments**

A CONSORT diagram will be generated to describe the flow of patients through the study, and will provide information about the number of patients who received Evolocumab treatment, the number of control patients (either consented on this study as a control or requested from the BTBR), and the number of patients who subsequently had a surgical procedure.

### **13.4 Primary Objective**

The primary objective of this study is to assess whether Evolocumab crosses the blood brain barrier (BBB) and is measurable in the resected or biopsied tumor specimens of patients with primary and recurrent glioma.

#### **13.4.1 Variable**

By means of mass spectrometry, the level of Evolocumab within the resected or biopsied brain tumor of a patient treated with one dose of Evolocumab will be assessed.

#### **13.4.2 Statistical Hypothesis, Model, and Method of Analysis**

The level of Evolocumab within the resected or biopsied tumor will be determined for patients treated with Evolocumab, and within a cohort of resected or biopsied control patients who were not treated with Evolocumab. Either a Wilcoxon rank sum test or a two-sample t-test will compare cohorts.

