## 6 OBJECTIVES AND ENDPOINTS

	Objective	Endpoint	Analysis
Primary	Evaluate the pharmacokinetics (PK) of evolocumab and whether it can cross the blood brain barrier (BBB) to accumulate intratumorally in patients with primary and recurrent glioma or glioblastoma	Presence of evolocumab detected in surgical resection or biopsy samples by means of mass spectrometry	See Section 13.4
Secondary	Compare lipid metabolism of tumor cells taken from resected or biopsied samples after dose of evolocumab to resected or biopsied samples obtained from s from untreated glioma patients.	Level of lipid metabolism within the resected or biopsied tumor as assessed via fluorescence-activated cell sorting (FACS)	See Section 13.5.1
Secondary	Compare MHC-I expression on tumor cells following administration of evolocumab to samples from untreated glioma patients with tissue	Extent of MHC-I expression within the resected or biopsied tumor, as assessed by fluorescence-activated cell sorting (FACS)	See Section 13.5.1
Secondary	Among patients treated with evolocumab, describe the strength of the association between serum and intratumoral levels of evolocumab. Peripheral blood samples to be taken before administration of evolocumab and at time of surgery or biopsy.	Correlation of serum and intratumoral levels of evolocumab	See Section 13.5.2 .
Exploratory	Describe the immune characteristics of tumor cells taken from resected or biopsied samples	Sequencing characteristics as assessed by multi-omics analysis, immune infiltration, and T cell profiling	See Section 13.6
Exploratory	Assess the activity of T cells isolated from tumor specimens in patients treated with or without evolocumab	Characterization of tumor-infiltrating lymphocytes (TILs) based on flow cytometry immunostaining of TILs for expression of markers of exhaustion (e.g., PD-1, Lag3, TIM3) and activation (CD137)	See Section 13.6

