## 10.4 Active Follow-up Period

### Days 4-14 – Surgical resection or biopsy

- Tumor tissue collection (applies to patients who consent to either arm of the study) – this tissue will be taken intraoperatively for pharmacokinetic LC-MS analysis to assess for the presence of evolocumab.
  - Sample will only be taken for analysis if greater than 20 mg of resected or biopsied tissue available (excess available beyond that required for histological analysis)
  - Sample to be aliquoted into 25 mg sections for resections and 10-20 mg (1-2 cores) for biopsies

Treatment arm only:

- Pharmacokinetic blood draw (5 mL, drawn at time of surgery or biopsy, i.e., PK draw may occur either immediately before or during surgery or biopsy)Error! Bookmark not defined.
- Adverse events monitoring

About 2 weeks following surgery or biopsy (treatment arm only)

- Physical and neurological exam
- Laboratory evaluations (obtained as part of standard post-operative labs)
  - CBC with differential
  - CMP
- Adverse events monitoring

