#### **13.4.3 Handling of missing values, censoring, and discontinuations**

Not applicable.

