#### **13.5.2 Secondary Objective #3: Serum and Intratumoral Levels of Evolocumab**

Among patients treated with evolocumab, the third secondary objective is an assessment of the relationship between serum and intratumoral levels of the drug. These assessments will be obtained at the time of surgical procedure. A scatterplot will graphically show the relationship between these two measures. Spearman's rank correlation will assess their association.

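### The primary endpoint is presence of evolocumab in the tumour, but the only planned primary analysis tests levels against undosed controls and reports no count of tumours with drug detected

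*Combined protocol and SAP*

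**What the plan says.** Section 6 gives the primary endpoint as "Presence of evolocumab detected in surgical resection or biopsy samples by means of mass spectrometry" and points to Section 13.4 for the analysis. Section 10.4 describes the tissue collection in the same terms: "this tissue will be taken intraoperatively for pharmacokinetic LC-MS analysis to assess for the presence of evolocumab". The objective restated in Section 13.4 is whether the drug "is measurable in the resected or biopsied tumor specimens of patients with primary and recurrent glioma".

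Section 13.4.1 then names a different kind of variable: "the level of Evolocumab within the resected or biopsied brain tumor of a patient treated with one dose of Evolocumab will be assessed". Section 13.4.2 determines the level in treated patients and in controls who received no evolocumab, and gives one analysis: "Either a Wilcoxon rank sum test or a two-sample t-test will compare cohorts". Synopsis 3.6 likewise frames the primary objective as a comparison of two cohorts, and Section 3.2 says openly that levels in treated tissue will be compared with those in controls once an assay has been developed.

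Section 13.4.3, headed "Handling of missing values, censoring, and discontinuations", is marked as not applicable. Section 3.3 plans a calibration curve in blank tumour homogenate and an enrichment step if it proves necessary. Section 13.8 bases the sample size on practical grounds, to allow descriptive analysis.

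**The concern.** A presence endpoint is naturally reported as a number: how many treated tumours had drug above a stated limit, with an interval. Section 13.4 does not plan that number. A group test against undosed patients answers a narrower question, whether treated levels tend to exceed background, and a significant result is compatible with drug in a minority of tumours or in all of them. Those two findings bear differently on the trial's stated purpose of judging whether repurposing evolocumab for glioma is worthwhile.

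Non-detects are foreseeable: controls received no drug, the tissue assay is still to be developed, and enrichment is held in reserve. How they enter the rank test affects the p-value when few treated tumours are positive, and no rule is given. A study sized for description thus has a test, but no descriptive estimate, for its primary endpoint.

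**Working it through.** The plan gives no alpha, power or detection rate, so there is no figure of its own to reproduce. The check asks what the planned test would return.

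**Inputs.** Treated n = 10 and controls m = 20 (Sections 3.3 and 7.1, both maxima). Assumed: two-sided 5%; no control above the limit; k of the 10 treated tumours above it.

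**Detection estimate.** k/10 with the Clopper-Pearson 95% interval.

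**Exact rank test, non-detects tied.** The k detected tumours hold the top k ranks, so the upper tail is C(10,k)/C(30,k). For k = 4 this is 210/27,405 = 0.0077. For k = 10 it is 1/C(30,10) = 3.3e-8. Ordering outcomes as Fisher's test does, this is also the two-sided p, because nothing in the other tail is as extreme. The other common convention doubles it.

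**Exact rank test, background kept as untied numbers.** The k detected tumours again hold the top k ranks. The other 10 - k treated tumours are taken as a random subset of the remaining 30 - k ranks. The table gives the median exact p over all rank orders and, in brackets, the share of orders with p <= 0.05.

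| Detected | Proportion (95% CI) | Tied, Fisher ordering | Tied, doubled tail | Untied, median p (share <= 0.05) |
|---|---|---|---|---|
| 2/10 | 20% (3%-56%) | 0.103 | 0.207 | 0.37 (11%) |
| 3/10 | 30% (7%-65%) | 0.030 | 0.059 | 0.20 (22%) |
| 4/10 | 40% (12%-74%) | 0.008 | 0.015 | 0.082 (39%) |
| 5/10 | 50% (19%-81%) | 0.0018 | 0.0035 | 0.028 (64%) |
| 6/10 | 60% (26%-88%) | 0.0004 | 0.0007 | 0.007 (88%) |
| 8/10 | 80% (44%-97%) | 7.7e-6 | 1.5e-5 | 1.6e-4 (100%) |
| 10/10 | 100% (69%-100%) | 3.3e-8 | 6.7e-8 | 6.7e-8 |

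**Normal approximation at 2/10, tied.** U = 2 x 20 + 8 x 20 x 0.5 = 120 against a mean of 100. With 28 values tied, the variance is (200/12) x [31 - (28^3 - 28)/(30 x 29)] = (200/12) x 5.8 = 96.7. Then z = 20/9.83 = 2.03 and p = 0.042; with continuity correction, z = 19.5/9.83 = 1.98 and p = 0.047. The exact p is 0.103.

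**Specificity check.** With 0/20 controls above the limit, the upper 95% limit is 1 - 0.025^(1/20) = 16.8%.

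**The case against.** The strongest reply is that the plan chose this comparison deliberately. Section 3.2 and synopsis 3.6 both state it, Section 3.3 says the drug will be quantified, and the Section 6 objective speaks of pharmacokinetics and accumulation. With an assay still to be built, showing levels above undosed background is a coherent way to show that drug is present. That stands: a reader might infer that the endpoint was switched by mistake or that the control comparison is invalid, and the documents support neither. What remains is that Section 6 refers a presence endpoint to a section that never reports presence.

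A reader might also infer that no limit will exist at all. The documents do not go that far. The calibration curve could supply one, and Section 3.3 refers its data analysis to a cited assay publication that was not available here. The supportable statement is that these documents state no limit and carry none into the analysis.

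It is tempting to contrast 3/10 with 10/10 as two significant results whose intervals do not overlap. That holds only under Fisher ordering; doubling the tail gives 0.059 at 3/10. At 4/10, significant under both conventions when non-detects are tied, the interval (12%-74%) does overlap that for 10/10 (69%-100%).

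Individual treated values will be visible: in Section 13.5.2, "A scatterplot will graphically show the relationship between these two measures". That plot is a secondary analysis and has no limit, count or interval.

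Finally, Section 10.4 says "Sample to be aliquoted into 25 mg sections for resections and 10-20 mg (1-2 cores) for biopsies", from which one might infer different detection limits by specimen type. Section 3.3 plans normalisation by a protein assay, which may reduce any difference, and limits by tissue input are a matter for assay validation. The point does not rest on them.

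**Conclusion.** The concern holds as a mismatch between endpoint and analysis, together with an omission; no figure in the plan is wrong. The planned test can show that some treated tumours exceed background. It cannot separate drug in 4 of 10 tumours from drug in all 10, other than by the size of a p-value, because both are significant when non-detects are tied.

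The further dependence on unstated choices (exact or approximate test, two-sided convention, treatment of below-limit readings) is confined to about 2 to 5 detections in 10. From about 6/10 the handling rarely changes the verdict, and the documents give no reason to expect one range over the other. The detection proportion does not depend on these choices once the limit is fixed.

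The sizes rest on an assumed two-sided 5% level, full recruitment of 10 and 20, and no control above the limit. Fewer assayed controls would change the p-values but not the treated detection interval. This is a cheap improvement that gives a better answer to the trial's own question.

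**What to change.** 1. In 13.4.1, 13.4.2 and synopsis 3.6, make the primary analysis the number and proportion of treated tumours with evolocumab above a named limit, with an exact (Clopper-Pearson) 95% interval. The denominator is dosed patients with an assayed resection or biopsy specimen. Amend 13.1 to match: its PK and PD set names resection only, although its next statement, on serum and intratumoral levels, admits biopsies.
2. Fix the limit from the planned blank-matrix calibration before treated samples are read. Say whether it is the limit of detection or of quantification, since Section 6 speaks of detection and 13.4 of measurability.
3. Report the proportion of controls above the same limit as a specificity check, using the number of controls actually assayed (0/20 would give an upper 95% limit of 17%).
4. Keep the level comparison as supportive: an exact rank test with non-detects tied at the lowest rank and the two-sided convention stated. Put this below-limit rule in 13.4.3 in place of the present entry.

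The cost is mainly wording, on data already planned, with no added patients or procedures; a few extra blank-matrix runs may be needed. The real downside is that the headline becomes a wide interval, for example 44%-97% at 8/10, in place of a small p-value.

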#### **13.4.3 Handling of missing values, censoring, and discontinuations**

Not applicable.

### **13.5 Secondary Objectives**

This study's three secondary objectives include a comparison of brain tumor tissues specimens with and without Evolocumab with respect to lipid metabolism, and tumor cells expressing MHC-I; and an assessment of the relationship between serum levels of evolocumab and intratumoral concentrations.

#### **13.5.1 Key Secondary Objectives #1and #2: Lipid Metabolism and Tumor Cells Expressing MHC-I**

The first two secondary objectives involve a comparison of the pharmacodynamics (PDs) of Evolocumab in treated patients relative to that observed in a control cohort of untreated patients. The characterization of the PD properties will include the following: (1) Lipid metabolism of tumor cells taken from resected or biopsied samples, and (2) Analysis of tumor cells expressing MHC-I will be performed by fluorescence-activated cell sorting (FACS). Analyses similar to those describe for the primary objective will be performed.

#### **13.5.2 Secondary Objective #3: Serum and Intratumoral Levels of Evolocumab**

Among patients treated with evolocumab, the third secondary objective is an assessment of the relationship between serum and intratumoral levels of the drug. These assessments will be obtained at the time of surgical procedure. A scatterplot will graphically show the relationship between these two measures. Spearman's rank correlation will assess their association.

### **13.6 Exploratory Objectives**

This study has two exploratory objectives: (1) To describe the immune characteristics of tumor cells taken from resected or biopsied samples, and (2) To assess the activity of T cells isolated from tumor specimens in patients treated with or without evolocumab.

*Exploratory Objective #1:* We hypothesize that evolocumab treatment will lead to global changes in pro-tumorigenic pathways and the reduction in PSCK9 levels and therefore will seek to determine the immune characteristics (multi-omics analysis, immune infiltration and T cell profiling) of tumor cells taken from resected or biopsied samples. To test this hypothesis, non-targeted quantitative LC-MS/MS will be performed on resected or biopsied tumors from n=10 treatment patients versus n=20 untreated control specimens. Furthermore, if PSCK9 is not among the proteins quantified by non-targeted LC-MS/MS, a more sensitive targeted LC-MS/MS analysis will be utilized as described for the PK analysis of evolocumab above. Bioinformatic analyses of differentially expressed proteins will utilize protein set enrichment, gene ontology (GO) annotations, and search tool from the retrieval of interactive genes/proteins (STRING).

Wilcoxon rank-sum test, or a two-sample t-test, will compare groups with respect to these endpoints. Given the number of comparisons that may be conducted in these exploratory analyses, adjustment for multiple comparisons will be made.

*Exploratory Objective #2:* Cells stained for expression of surface and nuclear markers of exhaustion (PD-1, Lag3, TIM3) and activation (CD137) will be characterized using flow cytometry. We will explore the potential to select and expand the non-exhausted CD137+ subset and examine their anti-tumor efficacy in samples from patients treated with or without evolocumab. Cytotoxicity determined by flow cytometry of stained tumor cells will be compared to no TIL exposure. Patient-derived neurospheres will be generated *in vitro* based on established protocols. Statistical methods described for exploratory objective #1 will be used.

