## 7 INVESTIGATIONAL PLAN

### 7.1 Study Design

This phase 0/surgical window of opportunity study is being conducted to assess if Evolocumab, a clinically approved drug for hypercholesterolemia, can cross the blood brain barrier and accumulate within the brain tumor of patients with glioma or glioblastoma. Study participants will include newly diagnosed or recurrent patients who are due to undergo resection or biopsy of their tumor. Up to 10 patients will be enrolled in the treatment arm of this study, while up to 20 patients will serve as controls.

**Study treatment arm:** Each eligible patient will receive 420 mg of Evolocumab subcutaneously (the maximum single dose) 4-14 days prior to surgical resection or biopsy of their tumor. Prior to injection of evolocumab (treatment arm only) and at time of surgery surgery, peripheral blood will be drawn to analyze serum levels of the drug (for comparison to intratumoral).

Following administration of Evolocumab and surgical procedure, patients in the treatment arm will be followed up for two weeks to observe for any evidence of side effects or toxicity. Although the safety profile of Evolocumab is well understood, the study will be paused and re-evaluated should any significant toxicities occur.

Patients can then proceed to standard of care treatment for their glioma following the trial, with no expected impediment caused by the use of Evolocumab.

**Control arm:** A control group of 20 patients who undergo craniotomy without Evolocumab treatment will be prospectively recruited to this study using similar eligibility criteria used to recruit patients to receive Evolocumab. If accrual of these controls is difficult, matched 2:1 (controls: cases) will be obtained from the BTBR (Pro00007434). The control arm will have peripheral blood drawn prior to their scheduled day of the surgical procedure or on the day of the surgical procedure. Patients who consent to participate as a control for this study will come off study after tissue is collected for research (if available) during their surgical procedure.

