### 7.3 Rationale for Correlative Studies

To compare the pharmacokinetics (PK) of evolocumab in treated patients, peripheral blood samples will be taken to compare serum concentrations of evolocumab to intratumoral concentrations. These are further detailed in Section 10.

Tumor-infiltrating lymphocytes (TILs) from tumor or liquid obtained from the surgical field will be dissociated into a single cell suspension or fragmented and TILs expanded as one batch following the TILs pre-rapid expansion protocol (preREP). The ability to successfully and reliably expand preREP TILs from lung cancer and glioblastoma samples has been previously demonstrated in Pro00106078. TILs, in general, display a profound degree of exhaustion. Therefore, cells will be stained for expression of surface and nuclear markers of exhaustion (PD-1, Lag3, TIM3) and activation (CD137) and differential levels assessed by flow cytometry. CD137 is upregulated on T cells during early activation immediately following interaction with tumor antigen in the Tumor Microenvironment (TME). We will explore the potential to select and expand the non-exhausted CD137+ subset and examine their anti-tumor efficacy in samples from patients treated with or without evolocumab. Autologous CD137+ TIL cell product will be co-cultured with disassociated CFSE labeled neurospheres for 24 and 48 hours. Cytotoxicity determined by flow cytometry of CFSE+ tumor cells will be compared to no TIL exposure. Patient-derived neurospheres will be generated *in vitro* based on established protocols .

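### If cytotoxicity with and without TILs is tested as Section 13.6 objective #2 is written, the only tests assigned ignore the likely within-patient pairing (minor)

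*Combined protocol and SAP*

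**What the plan says.** Section 13.6, exploratory objective #2, concerns the activity of T cells taken from the tumors of treated and untreated patients. For the killing assay it says: "Cytotoxicity determined by flow cytometry of stained tumor cells will be compared to no TIL exposure". The paragraph gives no test of its own and closes with: "Statistical methods described for exploratory objective #1 will be used".

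The methods it refers to are in the objective #1 text of the same section: "Wilcoxon rank-sum test, or a two-sample t-test, will compare groups with respect to these endpoints".

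Section 7.3 describes the assay: "Autologous CD137+ TIL cell product will be co-cultured with disassociated CFSE labeled neurospheres for 24 and 48 hours". It repeats the contrast: "Cytotoxicity determined by flow cytometry of CFSE+ tumor cells will be compared to no TIL exposure". Sections 7.3 and 13.6 both say that the neurospheres are patient-derived.

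No paired t-test, signed-rank test or within-patient model is named anywhere in Section 13.

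**The concern.** The rank-sum and two-sample t-tests treat the two sets of readings as coming from unrelated subjects. Here the effector cells are autologous and the target cells are grown from the patient's own tumor. The obvious no-TIL control is the same patient's neurospheres without TILs. Each patient would then supply one reading under each condition, which makes a pair.

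Neurosphere lines are likely to differ between patients in baseline viability and growth, and a pair shares that variation. An unpaired test counts the shared part as noise in the difference. With positive within-patient correlation its standard error is too large, its p-values are too large, and a real killing effect is more easily missed.

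The number of usable pairs is not assured, so efficiency has some value. Section 10.4 takes a sample only above 20 mg. Control patients "will come off study after tissue is collected for research (if available) during their surgical procedure". Obtaining the cells is itself tentative: "We will explore the potential to select and expand the non-exhausted CD137+ subset".

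**Working it through.** **Is there a figure to reproduce?** No. Section 13.8 says the sample size was chosen on practical grounds, and no alpha, effect size, SD or power is given for this contrast. Everything below illustrates with assumed values.

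**Inputs from the documents.** Planned patients: 10 treated and 20 control, so at most 30 pairs if every planned patient yields usable cells. Tests: two-sample t or rank-sum.

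**Assumed inputs.** One reading per condition per patient, bivariate normal with SD 1 in each condition; true shift 0.8 SD; two-sided 5%; no multiplicity adjustment; within-patient correlation rho from 0 to 0.7; 6, 10, 20 or 30 usable pairs.

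**Step 1: the standard error.** For n pairs with common SD s:

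- The two-sample t-test estimates the SE of the mean difference as s × sqrt(2/n).
- The true SE is s × sqrt(2(1 − rho)/n).
- The ratio of true to assumed SE is sqrt(1 − rho).

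At n = 10 and rho = 0.5, the assumed SE is sqrt(0.2) = 0.447, the true SE is sqrt(0.1) = 0.316, and the ratio is 0.707. The unpaired test works with an SE about 41% too large (0.447/0.316 = 1.41).

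**Step 2: paired t power at that point.** The noncentrality is 0.8/0.316 = 2.53 on 9 degrees of freedom, with critical value 2.262. Power is 0.62.

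**Step 3: unpaired against paired, by simulation** (40,000 runs per cell; the noncentral t distribution gives the same paired-t power to within 0.01).

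| Pairs | rho | Type I error, two-sample t | Power, two-sample t | Power, paired t |
|---|---|---|---|---|
| 6 | 0 | 0.05 | 0.24 | 0.21 |
| 6 | 0.5 | 0.012 | 0.19 | 0.36 |
| 10 | 0 | 0.05 | 0.39 | 0.36 |
| 10 | 0.3 | 0.02 | 0.38 | 0.48 |
| 10 | 0.5 | 0.01 | 0.37 | 0.62 |
| 10 | 0.7 | 0.002 | 0.35 | 0.83 |
| 20 | 0.5 | 0.01 | 0.76 | 0.92 |
| 30 | 0.5 | 0.01 | 0.93 | 0.99 |

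The paired t-test holds its type I error at about 0.05 throughout.

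**Step 4: rank tests.** At n = 10 and rho = 0.5, rank-sum has power 0.33 and signed-rank about 0.60. At n = 6, signed-rank is worse than rank-sum at rho 0 (about 0.14 vs 0.20), no better at rho 0.3 (0.18 vs 0.18), and ahead only from rho 0.5 (0.24 vs 0.16). The smallest two-sided exact signed-rank p-value with n pairs is 2/2^n. With five pairs this is 2/32 = 0.0625, so 5% significance cannot be reached; with six it is 2/64 = 0.031.

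**The case against.** The strongest reply is that no TIL versus no-TIL test is planned. Objective #2 is framed around treated and untreated patients, the borrowed sentence speaks of comparing groups, and the other group comparisons in Section 13 are between those two cohorts. On that reading the no-TIL wells are only the assay background, each patient contributes one value, and rank-sum or two-sample t between arms is valid. Section 6 supports this in part: its endpoint for the objective lists exhaustion and activation markers, not cytotoxicity. Section 13.8 describes the analysis as descriptive.

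This reading is plausible, and it is why the point is conditional. But no section says that no-TIL is only a reference, while the sentence as written names TIL versus no TIL as the comparison and the same paragraph assigns it the unpaired tests.

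A second reply is that the pairing is inferred. That is true: neither Section 7.3 nor Section 13.6 states that the no-TIL wells use the same patient's neurospheres. It is still the natural reading of an autologous assay with patient-derived targets.

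A third reply is that the size of the loss is hypothetical. This also stands. The correlation, the shift and the number of pairs are assumed, and at the planned maximum of 30 pairs the loss at rho 0.5 is small.

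A reader might infer three stronger things that are not supported:

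- **That false-positive claims are at risk.** With positive correlation the error runs the other way.
- **That the named tests are wrong for the objective as a whole.** They suit treated versus untreated comparisons.
- **That the loss is worst with the fewest pairs.** At rho 0.5 the absolute power loss is 0.36 − 0.19 = 0.17 at n = 6, 0.62 − 0.37 = 0.25 at n = 10, 0.92 − 0.76 = 0.16 at n = 20, and 0.99 − 0.93 = 0.06 at n = 30. Among these sizes it is largest at n = 10; only the relative loss is greatest at the smallest n.

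**Conclusion.** The point holds conditionally and is minor. If cytotoxicity with TILs is tested against no TIL exposure using the methods Section 13.6 assigns, and the readings are paired as Section 7.3 suggests, the analysis ignores the pairing. Under the assumed 0.8 SD shift and rho 0.5, that means a nominal 5% test running at about 1%, and with 10 pairs about 25 percentage points of power given up. With no correlation nothing is lost, and the unpaired t-test is then slightly better. The conclusion rests on two inferences, that the contrast will be formally tested and that both readings come from the same patient, and on positive correlation.

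The documents do not show that a wrong test will in fact be run; they leave that open. The objective is exploratory, cytotoxicity is not in its Section 6 endpoint, and no primary or secondary conclusion changes.

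**What to change.** In Section 13.6, objective #2:

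1. State whether TIL versus no TIL exposure is tested or serves only as the assay reference, and whether both readings use the same patient's neurospheres.
2. If it is tested, use a paired t-test, or a Wilcoxon signed-rank test, on each patient's two values.
3. Keep rank-sum or two-sample t for treated versus untreated comparisons.
4. When pairs are few, prefer the paired t-test or report descriptively. With five or fewer pairs signed-rank cannot reach two-sided p < 0.05.

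The cost is a few sentences, with the same samples and data. The paired t-test loses a little power when the correlation is near zero (0.21 vs 0.24 at six pairs; 0.36 vs 0.39 at ten). Signed-rank gives up more at six pairs (about 0.14 vs 0.20 at rho 0, with no gain at rho 0.3), which is the reason for the preference in item 4.
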